10.2. Exclusion Criteria

A subject will not be eligible for the study if he/she meets any of the following criteria:

1. Currently pregnant, nursing, or planning to become pregnant during the study or within 1 month after study drug administration. Female subjects must be surgically sterile or at least 2 years menopausal, or using an acceptable method of birth control. If of child-bearing potential, must have a documented negative pregnancy test within 24 hours before surgery.
2. Planned concurrent surgical procedure (e.g., bilateral TKA).
3. Use of any of the following medications within the times specified before surgery: long-acting opioid medication, NSAIDs, or aspirin (except low-dose aspirin used for cardioprotection or acetaminophen) within 3 days, or any opioid medication within 24 hours.
4. Concurrent painful physical condition or concurrent surgery that may require analgesic treatment (such as an NSAID or opioid) in the postsurgical period for pain that is not strictly related to the surgical site administered study treatment, and which may confound the postsurgical assessments (e.g., significant pain from other joints including the non-index knee joint, chronic neuropathic pain, prior contralateral TKA, concurrent foot surgery).
5. Initiation of treatment with any of the following medications within 1 month of study drug administration or if the medication(s) are being given to control pain: selective serotonin reuptake inhibitors (SSRIs), selective norepinephrine reuptake inhibitors (SNRIs), gabapentin, pregabalin (Lyrica[®]), or duloxetine (Cymbalta[®]).
6. Current use of systemic glucocorticosteroids within 1 month of enrollment in this study.
7. Body weight < 50 kilograms (110 pounds) or a body mass index ≥ 40 kg/m².
8. Contraindication to hydromorphone, oxycodone, or bupivacaine.

9. Administration of an investigational drug within 30 days or 5 elimination half-lives of such investigational drug, whichever is longer, prior to study drug administration, or planned administration of another investigational product or procedure during the subject's participation in this study.
10. Previous participation in a liposome bupivacaine study.
11. History of, suspected, or known addiction to or abuse of illicit drug(s), prescription medicine(s), or alcohol within the past 2 years.
12. Failure to pass the urine drug screen.
13. Uncontrolled anxiety, schizophrenia, or other psychiatric disorder that, in the opinion of the Investigator, could interfere with study assessments or compliance.
14. Malignancy in the last 2 years, with the exception of non-metastatic basal cell or squamous cell carcinoma of the skin or localized carcinoma in situ of the cervix.
15. Current or historical evidence of any clinically significant disease or condition, especially cardiovascular or neurological conditions that, in the opinion of the Investigator, may increase the risk of surgery or complicate the subject's postsurgical course.
16. Significant medical conditions or laboratory results that, in the opinion of the Investigator, indicate an increased vulnerability to study drugs and procedures.
17. Subjects who are planned to receive Entereg[®] (alvimopan).
18. Subjects who will receive prophylactic antiemetics or planned postsurgical antiemetics given without regard to the subject's emesis needs.
19. Use of dexmedetomidine HCl (Precedex[®]) within 3 days of surgery.

10.3. Removal of Subjects from Therapy or Assessment

Every reasonable effort should be made to maintain subject compliance and participation in the study. Reasons for discontinuation of any subject from the study will be recorded.

Subjects who withdraw from the study postsurgically should be followed for AEs. All AEs that occur through Day 30 after surgery must be recorded. If a subject who withdraws from the study has an ongoing AE, every effort must be made to follow such events until satisfactory resolution is obtained, or further follow-up is otherwise no longer warranted.

Safety assessments performed during the early termination visit should include the neurological examination, cold test, 20-meter walk test, and collection of a blood sample for PK analysis, if possible.

10.3.1. Withdrawal Secondary to Adverse Events

If a subject experiences an AE that renders him/her incapable of continuing with the remaining study assessments, then he/she will be discontinued from further participation in the study. A final evaluation should be performed so that the subject's study participation can be terminated in a safe and orderly manner (see [Section 10.3](#)).

10.3.2. Voluntary or Study Investigator Withdrawal

Subjects are free to discontinue from the study at any time, without prejudice to future treatment. Nevertheless, subjects will be encouraged to complete at least the study safety assessments. In addition, a subject may be discontinued from the study if he/she refuses to comply with study procedures. Reasons for discontinuation from the study will be recorded.

If a subject is discontinued by the Investigator or voluntarily withdraws from the study after receiving liposome bupivacaine, he/she should be followed for AEs (see [Section 10.3](#)). A final evaluation should be performed so that the subject can be terminated in a safe and orderly manner.

11. TREATMENTS

11.1. Treatment to be Administered

Study Drug

Subjects will receive a single dose injection femoral block with either one of three doses of liposome bupivacaine (67, 133, or 266 mg) or placebo (preservative-free normal saline) in 20 mL volume under ultrasound guidance according to the randomization schedule. Preservative-free normal saline will be added to the 67 mg and 133 mg doses of study drug to achieve a volume of 20 mL (i.e., 15 mL of saline will be added to the 67 mg dose [5 mL] of liposome bupivacaine and 10 mL of saline will be added to the 133 mg dose [10 mL]). Study drug administration will be performed by study personnel who are NOT involved with protocol-specific, postsurgical assessments.

Rescue Medication

Subjects should only receive rescue medication upon request, as needed.

The first rescue medication will consist of IV hydromorphone 0.5 mg, which will be administered once via bolus only. At this time, the PCA should be loaded with opioid (morphine or hydromorphone only).

The second rescue medication will consist of an on-demand PCA-administered opioid (morphine or hydromorphone). The PCA pump will be programmed to deliver either on-demand morphine or on-demand hydromorphone boluses at a dose and lockout interval consistent with the site's standard practice. A continuous infusion (background or basal rate) of morphine or hydromorphone is not permitted. If the subject's pain is excessive or pain control is inadequate, then the bolus dose may be adjusted according to local hospital practices; however, **adding a basal rate is prohibited**. Once the subject is tolerating PO medication, PO immediate-release oxycodone may be administered (but not more than 10 mg every 4 hours).

If a subject's pain is inadequately controlled by opioids, a third rescue, a femoral nerve block, consisting of conventional bupivacaine HCl at a concentration of 0.125% (1.25 mg/mL) at a rate of 8 mL per hour for up to 12 hours will be administered via the previously placed femoral nerve catheter.

No other analgesic agents, including NSAIDs, are allowed during the 72-hour observation period or until the subject is withdrawn from the study, whichever is sooner. Subjects who do not achieve adequate pain relief with this regimen will be withdrawn from the study and followed for AEs per [Section 10.3](#).

11.1.1. Administration Technique

Study drug (liposome bupivacaine or placebo) will be administered under ultrasound guidance by the anesthesiologist into the femoral nerve as described below (adopted from [Mariano 2009](#)).

Patients will have their femoral nerve located by ultrasound guidance alone. The recommended method is as follows: With a linear array transducer in a sterile sleeve, the femoral nerve will be identified in a transverse (short-axis) view at the inguinal crease. In a transverse view, the

internal appearance of the peripheral nerve bundle is a mixture of hypoechoic neural tissue (fascicles) and hyperechoic connective tissue (perineurium and epineurium). Once the optimal image of the femoral nerve is obtained, a local anesthetic skin wheal will be raised lateral to the ultrasound transducer. A needle will be inserted through the skin wheal and directed medially in plane beneath the ultrasound transducer toward the femoral nerve. The study drug (20 mL) will be injected posterior to the femoral nerve *via* the needle. A flexible epidural-type catheter will then be placed through the length of the needle and advanced 5 cm beyond the needle tip. Once the catheter has been inserted, the needle itself will be withdrawn over the catheter. The catheter tip position will be assessed by injecting 1 mL of air *via* the catheter under ultrasound guidance with the appearance of hyperechoic air bubbles posterior to the femoral nerve confirming proper catheter placement (and replaced, if necessary). Because the in-plane ultrasound-guided needle placement technique effectively “tunnels” the catheter in a lateral-to-medial direction under the transducer, the catheter will not be tunneled further. The catheter will be secured with sterile liquid adhesive, a clear occlusive dressing, and an anchoring device to affix the catheter hub to the subject. After negative aspiration, 2 mL of normal saline will be injected *via* the catheter to help ensure future patency.

11.1.2. Study Drug Administration Considerations

Since there is a potential risk of severe adverse effects associated with the administration of bupivacaine, the study site must be equipped to manage subjects with any evidence of cardiac toxicity.

Administration of additional local anesthetics including bupivacaine or lidocaine is prohibited except where specified for spinal anesthesia or rescue. Bupivacaine cannot be used as the spinal anesthetic. Liposome bupivacaine may not be administered to a subject if it has been held in a syringe for more than 4 hours after preparation. In order to prevent the study drug from settling, gently inverting and re-inverting the syringe several times prior to administration is recommended.

11.2. Identity of Investigational Product(s)

11.2.1. Description of Liposome Bupivacaine

Liposome bupivacaine is formulated as a sterile, non-pyrogenic, white to off-white, preservative-free, homogeneous suspension of bupivacaine encapsulated into multivesicular lipid-based particles (the DepoFoam drug delivery system). Bupivacaine is present at a nominal concentration of 13.3 mg/mL. Liposome bupivacaine will be provided in 20 mL, 1.3% (13.3 mg/mL) single-use, clear glass vials.

11.2.2. Description of Reference Product

Placebo will consist of preservative-free normal saline for injection and will be supplied by the study sites. Subjects in the placebo group will receive 20 mL of placebo.

11.2.3. Description of Diluents

Preservative-free normal saline for injection will be added to the 67 mg (5 mL) and 133 mg (10 mL) doses of study drug to achieve a volume of 20 mL.

11.3. Method of Assigning Subjects to Treatment

11.3.1. Randomization Scheme

In Part 1 of the study, approximately 100 subjects (25 per treatment arm) will be randomized to receive a single dose injection femoral block with either one of three doses of liposome bupivacaine (67, 133, or 266 mg) or placebo.

In Part 2 of the study, approximately 180 subjects (randomized 1:1, resulting in approximately 90 liposome bupivacaine subjects and 90 placebo subjects) will be randomized to receive single dose injection femoral nerve block with the selected dose level (i.e., 67, 133, or 266 mg liposome bupivacaine) or placebo.

The randomization code will be generated by a centralized randomization system, which will also be used to communicate subject randomizations to study sites. All randomized subjects will have both a unique subject identifier and a unique random code identifier. No subject or random code identifiers are to be reused once assigned.

11.3.2. Randomization Procedures

Once a subject is identified as being qualified for the study per the eligibility criteria (see [Section 10.1](#) and [Section 10.2](#)), and is at the study site for surgery, the research pharmacist or designee will contact the centralized randomization service to obtain a randomization assignment (4-digit random code identifier). The subject will be considered randomized into the study once the assignment is received.

11.3.3. Replacement of Subjects

Subjects who are randomized but are withdrawn from the study before receiving study drug or do not undergo the planned surgical procedure may be replaced. Once assigned, subject numbers will not be reused; subjects enrolled to replace those who withdraw will be assigned a unique subject number and randomized to treatment according to the procedures outlined above.

11.4. Selection of Doses in the Study

During the clinical development of liposome bupivacaine, single doses ranging from 9 mg to 665 mg were safely administered via various routes. Pharmacokinetic studies have shown that because liposome bupivacaine releases bupivacaine gradually as the lipid structure breaks down, administration of liposome bupivacaine 266 mg results in a maximum plasma concentration equivalent to that seen with standard bupivacaine 100 mg. Based on this experience, a similar maximum total dose was deemed appropriate for this study.

During Part 1 of the current study, subjects will receive a single dose femoral nerve block with one of three dose levels of liposome bupivacaine (67, 133, or 266 mg) or placebo. During Part 2 of the study, subjects will receive a single dose injection femoral nerve block with the selected dose level of liposome bupivacaine (i.e., 67, 133, or 266 mg) or placebo.

11.5. Blinding

11.5.1. Blinding Procedures

Liposome bupivacaine and placebo are visually distinguishable; therefore, to maintain the double-blind study design, the Principal Investigator and any study personnel involved in protocol-specific postsurgical assessments will remain blinded to treatment assignment. Only unblinded study personnel who are NOT involved with protocol-specific, postsurgical assessments may prepare or administer the study drug. Staff members conducting study-specific, postsurgical assessments and the subjects will remain blinded to the assigned treatment throughout the study. If a subject experiences an SAE, Pacira will not automatically unblind the subject's treatment, unless it is necessary to manage treatment of the SAE. Expedited SAEs will be unblinded by Pacira for regulatory reporting purposes.

Unblinded randomization assignments will be provided via a randomization system. At each site, only the individual(s) who are identified in the randomization system to receive unblinded randomization assignments will be responsible for preparing study drug.

Site surveys suggest that study sites will vary in their standard (and feasible) procedures for preparing sterile study drug in a blinded fashion. Therefore, each site will be responsible for providing their written blinding procedures for study drug preparation, transportation, and administration that will ensure that the blind is maintained throughout each of these steps. This documentation will be made available to Pacira for review before the site enrolls a subject into the study. Assignment of blinded and unblinded responsibilities regarding the preparation of study drug should take into account that **liposome bupivacaine may not be held in a syringe for more than 4 hours after preparation for administration.**

The presurgical administration of study drug will be recorded using the minimal amount of information necessary to avoid unblinding staff who will be participating in blinded procedures.

No crossover will be permitted between the blinded and unblinded study site personnel during the study period. The assignment of site monitors will also be segregated. Blinded monitors will review case report forms (CRFs), clinic charts, and all other study-related documents that do not disclose the allocation of study treatment. Care should be taken in recording and review of operating room records to not record information in an unblinded fashion. Pharmacy or any other clinic records providing unblinded information (e.g., randomization, study drug preparation, study drug accountability, study drug administration) will be reviewed by specialized unblinded monitors who will notify Pacira of treatment noncompliance.

11.5.2. Unblinding Procedures

Subject treatment assignments should not be unblinded during the study by blinded study personnel. The Investigator will have the ability to unblind a subject if he or she feels that subject safety warrants such unblinding. However, the Investigator should discuss the safety issues with the Medical Monitor before attempting such unblinding, if possible. Any unblinding will be documented through immediate notification of the Pacira study team and the Investigator. Any accidental unblinding events (i.e., through mishaps in the operating room or miscommunication among study staff) must be reported to Pacira immediately.

Only designated staff at Pacira will have the option to unblind treatment assignment through the randomization system, which will be designed to document such a transaction and notify the lead member of each functional group that such a transaction occurred.

Any incidence(s) of unblinding will be noted in the clinical study report with a full discussion of the events leading to the decision to unblind.

11.6. Prior and Concomitant Therapy and Medications

11.6.1. Prior and Concomitant Medications and Therapy

Permitted Prior Medications and Therapy

- Low-dose aspirin for cardioprotection.
- Acetaminophen use is permitted up to the time of surgery.

Restricted Prior Medications and Therapy

- Systemic glucocorticosteroids are not permitted within 1 month of enrollment into this study.
- Initiation of treatment with any of the following medications within 1 month of study drug administration or if the medication(s) are being given to control pain is not permitted: SSRIs, SNRIs, gabapentin, pregabalin (Lyrica), or duloxetine (Cymbalta).
- Long-acting opioid medications, NSAIDs, or aspirin (except for low-dose aspirin used for cardioprotection or acetaminophen) are not permitted within 3 days of study drug administration.
- Dexmedetomidine HCl (Precedex) use is not permitted within 3 days of surgery.
- No opioid medications are permitted within 24 hours of study drug administration.

Concomitant medications

All medications taken within 3 days of study drug administration and up to 72 hours after the end of surgery or until the subject is withdrawn from the study, whichever is sooner, will be recorded on the CRF. Any medications administered in association with AEs occurring during the study will be recorded through Day 30.

11.6.2. Permitted and Restricted Therapy or Medications During Surgery

Permitted

- Short and ultra-short acting opioids (e.g., fentanyl) will be allowed during surgery.

Restricted

- Bupivacaine cannot be used as the spinal anesthetic.
- No agents are to be admixed with liposome bupivacaine (e.g., epinephrine, dexamethasone, and clonidine).

- Lidocaine and other local anesthetics will not be permitted to be locally administered during the surgery because they are known to interact with liposome bupivacaine resulting in the displacement of bupivacaine and elevated plasma levels.
- Intrathecal opioids.
- The use of opioids other than fentanyl (e.g., morphine, hydromorphone HCl), acetaminophen, ketorolac, or other NSAIDs will not be permitted intraoperatively except for emergency use to treat an AE.
- Entereg (alvimopan) use is prohibited.
- Prophylactic antiemetics or planned postsurgical antiemetics given without regard to the subject's emesis needs is prohibited.

11.6.3. Permitted and Restricted Therapy or Medications After Surgery through 72 Hours After Surgery

Permitted

- Rescue medication use is permitted as described in [Section 11](#).

Restricted

- No other analgesics are permitted within 72 hours after surgery.
- Entereg (alvimopan) use is prohibited.
- Prophylactic antiemetics or planned postsurgical antiemetics given without regard to the subject's emesis needs.
- Dexmedetomidine HCl (Precedex) use is prohibited.

For study purposes, it is important to standardize pain management modalities during the first 72 hours following study drug administration. Therefore, the study staff must adhere closely to the treatment options and requirements noted in the protocol. After 72 hours, the analgesic regimen may be adjusted for each subject individually, as deemed appropriate by the physician responsible for the postsurgical care.

All concomitant medication will be recorded through 72 hours after the end of surgery or until the subject is withdrawn from the study, whichever is sooner.

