
Table 1. Time and Events Schedule of Study Procedures

	Screen Visit	Day-1 to Day 1 ¹	15min	30min	1h	2h	4h	8h	12h	18h	24h	30h	36h	42h	48h	54h	60h	72h	Day 30
	Time Window	Within 30 days	±5 min	±5 min	±5 min	±15 min	±15 min	±30 min	±30 min	±1h	±1h	±1h	±1h	±2h	±2h	±2h	±2h	±4h	±4d
Obtain signed informed consent	X																		
Assess/confirm eligibility	X	X																	
Medical/surgical history	X	X																	
Demographics and baseline characteristics	X																		
Pregnancy test (for women of childbearing potential only)		X																	
Urine drug screen		X																	
Physical examination		X																	
Vital signs ²	X	X		X	X	X													
Perform neurological assessment ³		X	X	X	X	X	X	X	X	X	X	X	X	X	X		X	X	
Perform cardiac assessment (electrocardiogram recordings) ⁴			←-----→																
Perform sensory function assessment (cold test) ⁵		X			X	X		X		X		X		X		X		X	
Perform motor function assessment (20-meter walk test)	X										X							X	X
Randomize subject and prepare study drug		X																	
Administer study drug within 2 hours of surgery; record start and stop time		X																	
Record intraoperative opioids administered and dose		X																	
Place femoral nerve catheter and install PCA pump (prior to the completion of surgery)		X																	
Conduct pain intensity assessments (NRS-R, NRS-A) ⁶		X			X	X	X	X		X		X		X		X		X	X
Record times and amounts of rescue medication administered			←-----→																
Complete OBAS questionnaire											X				X			X	
Part 1 only (specific sites): Collect scheduled PK blood sample ⁷		X	X	X	X	X	X	X	X	X	X	X	X	X	X	X	X	X	
Subject satisfaction with postsurgical pain control																		X	X
Part 1 only Question subject re: predefined treatment-emergent ORAEs																		X	
Physician satisfaction with return of sensory/motor function																		X	X
Record concomitant medications ⁸			←-----→																
Record AEs (starting at randomization) ⁹			←-----→																

Abbreviations: AE = adverse event; d = day; min = minutes; NRS-A = numeric rating scale with activity; NRS-R = numeric rating scale at rest; OBAS = overall benefit of analgesia score; OR = operating room; ORAEs = opioid-related adverse events; PCA = patient-controlled analgesia; PK = pharmacokinetic.

* Postsurgical efficacy assessments will be conducted at the time points specified *after the end of surgery*.

¹ Before study drug administration.

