² Measure vital signs (heart rate and blood pressure) after subject has rested in supine position for at least 5 minutes.

³ If the neurological assessment reveals a neurological event that the Investigator believes may be associated with high levels of systemic bupivacaine, an unscheduled PK blood sample should be collected at the time that the event is noted.

⁴ Electrocardiogram testing should begin approximately 1 hour prior to study drug administration and continue through 72 hours after study drug administration.

- ⁵ Sensory function will be assessed at baseline, when the subject wakes up after surgery (general surgery subjects only), and at 2, 4, 12, 24, 36, 48, 60, and 72 hours after the end of surgery, or until the subject's sensitivity to cold is demonstrated on two consecutive evaluations.
- ⁶ Also record NRS pain intensity scores at first request for rescue pain medication.
- ⁷ Collect blood samples for PK analysis from subjects at specific sites during Part 1 of the study at baseline, 15 minutes, 30 minutes, and 1, 2, 4, 8, 12, 24, 36, 48, 60, and 72 hours *after the beginning of study drug administration*. Blood samples should be collected even if the subject is not yet in surgery or is still in surgery.
- ⁸ Instruct subject to discontinue prohibited medications. Record date/time of all medications starting 3 days prior to surgery through 72 hours after surgery. Record medications administered for treatment of an AE through Day 30.
- ⁹ If a cardiac or neurological event occurs during Part 1 or Part 2 of the study that the Investigator believes may be associated with high levels of systemic bupivacaine, an unscheduled PK blood sample should be collected at the time that the event is noted.

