13.1. Instructions for Conducting Procedures and Measures

With the exception of the PK assessments (which will be conducted after the beginning of study drug administration), all assessments conducted after baseline will be timed from the end of surgery. Day 1 is defined as the day on which study drug is administered. The beginning of surgery is defined as the time of the first incision. The end of surgery is defined as the time of the last suture/staple. Postsurgical is defined as after the end of surgery.

Subjects will be hospitalized for at least 72 hours after surgery; therefore, postsurgical analgesia and collection of study data through the primary endpoint will take place under the supervision of study staff.

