13.5. Procedures After Surgery Through 72 Hours

Part 1 Only

- Question subject regarding the predefined treatment-emergent opioid-related AEs at 72 hours after surgery (see [Appendix 6](#)).
- Collect scheduled blood samples for PK analysis at specific sites only per [Section 12.3](#).

Parts 1 and 2

- Administer rescue medication for breakthrough pain per [Section 11](#).
- Load PCA pump with morphine or hydromorphone if IV hydromorphone 0.5 mg × 1 bolus is administered.
- Record date, time, and amount of all rescue medication administered (IV hydromorphone bolus, PCA opioid, oxycodone, and/or conventional bupivacaine HCl) through 72 hours after surgery.
- Record subject's assessment of pain intensity using the NRS-R followed by the NRS-A at the following time points: 2, 4, 8, 12, 24, 36, 48, 60, and 72 hours after surgery and at first request for rescue pain medication, if applicable (see [Appendix 1](#)).
- Perform neurological assessment at 15 minutes, 30 minutes, and 1, 2, 4, 8, 12, 18, 24, 30, 36, 42, 48, 60, and 72 hours after surgery per [Section 13.1.3](#) (see [Appendix 2](#)).
- Perform cardiac assessment (i.e., 12-lead digital ECG recordings) through 72 hours after study drug administration.
- Perform sensory function assessment (i.e., cold test) when the subject wakes up after surgery (general anesthesia subjects only), and at 2, 4, 12, 24, 36, 48, 60, and 72 hours after surgery, or until the subject's sensitivity to cold has returned to the baseline level in two consecutive evaluations per [Section 13.1.5](#).
- Perform motor function assessment (i.e., ability of subject to perform a 20-meter walk, unassisted with the optional use of a 4-legged walker) at 24 hours and 72 hours per [Section 13.1.6](#).
- Measure vital signs (heart rate and blood pressure) after subject has rested for at least 5 minutes in the supine position at 30 minutes, 1 hour, and 2 hours after surgery.
- Complete OBAS questionnaire (see [Appendix 3](#)) at 24, 48, and 72 hours after surgery.
- Obtain overall rating of subject satisfaction with postsurgical pain control using the Likert scale at 72 hours after surgery (see [Appendix 4](#)).
- Record AEs and any treatment(s) for the events.

- If a cardiac or neurological event occurs during Part 1 or Part 2 of the study that the Investigator believes may be associated with high levels of systemic bupivacaine, an unscheduled PK blood sample should be collected at the time that the event is noted.

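### The 72 h pain score may be taken up to 76 h after surgery, but analgesics need be recorded only to 72 h, so wWOCF may miss a dose given before a late score

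*Protocol*

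**What the plan says.** **Timing of the score.** Protocol Table 1 allows ±4 h around the 72 h assessment, and Protocol 13.1 times assessments from the end of surgery. A score at 76 h is within protocol.

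**Recording of medication.** For rescue, Protocol 13.5 asks for dates, times and amounts ("IV hydromorphone bolus, PCA opioid, oxycodone, and/or conventional bupivacaine HCl) through 72 hours after surgery"). For other drugs, Protocol 11.6.1 asks for recording "up to 72 hours after the end of surgery or until the subject is withdrawn from the study", Protocol 11.6.3 says "All concomitant medication will be recorded through 72 hours after the end of surgery", and note 8 to Table 1 says "Record date/time of all medications starting 3 days prior to surgery through 72 hours after surgery". The one later requirement, in 11.6.1, is "Any medications administered in association with AEs occurring during the study will be recorded through Day 30".

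**Analgesia from 72 h.** Protocol 11.6.3 adds: "After 72 hours, the analgesic regimen may be adjusted for each subject individually". I found no rule that the 72 h score must come before such a change.

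**Use of the score.** SAP 7.1.1 keeps a score taken after 72 h. It interpolates between the 60 h and late scores to obtain a value at 72 h, once the SAP 7.1.2 imputation has been done. SAP 7.1.2 replaces scores that fall inside the window of a rescue drug: 6 h for oral oxycodone, 4 h for IV morphine, 2 h for IV hydromorphone, and until 12 h after the end of a bupivacaine infusion. Drugs without a listed window get one before the blind is broken.

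**The concern.** wWOCF is how the primary AUC deals with scores taken under rescue, and it can act only on a dose that is in the data. Between 72 h and a late score the plan permits new analgesia, does not require it to be recorded, and still uses the resulting score. A score lowered by such a dose would enter the AUC unreplaced, whereas the same situation at 60 h would trigger replacement.

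The AUCs exposed are the primary NRS-R AUC through 72 h, the tertiary NRS-R AUC from 48 to 72 h, and the NRS-A AUC through 72 h. Scores analysed by time point are not exposed, because wWOCF is specified only for AUC (Protocol 15.6.3.1, SAP 7.1.2). Opioid consumption through 72 h and time to first opioid rescue are not exposed either, because both stop at 72 h. The one sensitivity analysis in SAP 7.6.2.1 excludes subjects with PCA interval data and does not address this gap.

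**Working it through.** **1. The plan's own figure.** Protocol 15.3 gives a difference of 61, SD 104, 90 per arm and two-sided 0.05, with stated power above 97%. SE = 104 × √(2/90) = 15.50. The noncentral t with 178 df gives 97.5% (normal approximation 97.6%). The stated power reproduces and is not in dispute.

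**2. Weight of a late score.** Let the previous score be taken at p hours and the late score at T > 72. The value at 72 h is S(p) + [S(T) − S(p)] × (72 − p)/(T − p). The trapezoid from p to 72 has area (72 − p)/2 × [S(p) + S(72)]. One point of error in S(T) therefore changes the AUC by

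w = (72 − p)² / [2(T − p)].

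- p = 60: T = 73, 144/26 = 5.54; T = 74, 144/28 = 5.14; T = 75, 144/30 = 4.80; T = 76, 144/32 = 4.50.
- p = 58: 196/30 = 6.53 at T = 73, down to 196/36 = 5.44 at T = 76.
- p = 62: 100/22 = 4.55 at T = 73, down to 100/28 = 3.57 at T = 76.

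The values 58 and 62 are the ends of the ±2 h window at 60 h. With p = 60, an on-time 72 h score has weight 6, so a score at 76 h keeps 4.50/6 = 75% of it.

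**3. When an earlier recorded dose already covers the score.** With a last dose at 72 h, cover ends at 72 + 2 = 74 h for IV hydromorphone, 72 + 4 = 76 h for IV morphine and 72 + 6 = 78 h for oxycodone. A subject taking oxycodone every 4 h has a recorded dose at 68 h or later and is covered to at least 68 + 6 = 74 h. A bupivacaine infusion ending at 64 h or later covers 64 + 12 = 76 h. Under SAP 7.1.2 a late score already above the worst pre-rescue value would not be overwritten either.

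**4. Effect on an arm mean.** The documents give neither the share affected nor the size of the error. Assume the late score is 2 points below what wWOCF would have given. Shift = share × 2 × w.

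| Share of one arm | p = 60, T = 73-76 | p = 58-62, T = 73-76 |
|---|---|---|
| 10% | 0.90-1.11 | 0.71-1.31 |
| 25% | 2.25-2.77 | 1.79-3.27 |

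The full range, 0.71-3.27 NRS-hours, is 0.71/15.50 = 0.05 to 3.27/15.50 = 0.21 SE, or 1.2-5.4% of 61. With p = 60, if the shift shrinks the difference, power is 96.2-97.1% instead of 97.5%.

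**5. Both arms affected.** Only the difference in shares matters. With 25% of placebo and 10% of active, p = 60, the net shift is 0.15 × 2 × (4.50 to 5.54) = 1.35-1.66 NRS-hours, 0.09-0.11 SE, power 96.8-96.9%. With equal shares it is zero. If the active arm were affected more, the sign reverses.

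**6. Scaling.** The shift is proportional to the assumed error. A harsher assumption of 5 points, with 30% of placebo and 10% of active affected, gives 0.20 × 5 × (4.50 to 5.54) = 4.50-5.54 NRS-hours and power of 94.5-95.2%.

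**The case against.** **The 72 h limit may mean the 72 h visit.** Protocol 13.5 contains the 72 h score itself, whose window runs to 76 h, so its heading can be read as including that visit. Protocol 13.1 says "collection of study data through the primary endpoint will take place under the supervision of study staff". SAP 7.6.2.2 cuts transdermal fentanyl at its end time or 72 h, which suggests that later times can be in the data. The Table 1 row "Record times and amounts of rescue medication administered" has lost its end point in the text available to me, and the CRFs were not available. This stands as a reason to write that a dose may go unrecorded, not that it will. Protocol 11.6.1 and 11.6.3 count from the end of surgery, which favours the clock reading.

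**The doses can be recovered.** A reader might infer that an unrecorded dose is lost for good. The documents do not support that. SAP 7.1.3 expects rescue data to be complete, with queries and then conservative case-by-case imputation for gaps, and Protocol 11.5.1 has monitors review clinic charts. Subjects scored after 72 h with no covering window can be identified from Listings 16.5.1.1 and 16.5.2.1 to 16.5.2.3. What remains is that a dose outside the required recording period does not show up as missing, so nothing prompts the query.

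**Analgesia after 72 h is ordinary care, not rescue, and falls outside the endpoint interval.** The documents do not show that the replaced value is closer to the true pain at 72 h than the observed one, so the 2-point error measures departure from the plan's own rule, not from truth. Still, SAP 7.1.2 puts no 72 h cut-off on the doses that open a window, and SAP 7.1.1 uses the late score to obtain the 72 h value.

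**The effect is negligible.** Largely accepted. A subject must be scored late, dosed between 72 h and the score, not recorded, and not covered by an earlier window. Recording rules and windows are the same in both arms.

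**Conclusion.** The gap is in the text: a permitted scoring time runs up to 4 h past the required recording time, and the primary AUC uses the score. Where an analgesic falls in that interval and goes unrecorded, wWOCF will not act on the score unless an earlier window covers it.

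The size is small: about 0.7-3.3 NRS-hours against 61 (0.05-0.21 SE), resting entirely on the assumed 10-25% of one arm and 2-point error. It is zero with equal exposure. If placebo subjects receive more analgesia at that point, their AUC is lowered and the bias is conservative.

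A reader might infer that the primary result is materially biased or the trial underpowered. The documents do not support either: they give no affected share, no error size and no evidence of imbalance between arms. This is a data-collection point worth closing because closing it is cheap.

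**What to change.** 1. In Protocol 13.5, 11.6.1, 11.6.3 and note 8 to Table 1, require all analgesics to be recorded with times until 72 h after surgery or until the actual 72 h NRS assessment, whichever is later. This also settles the clock-or-visit question.
2. In SAP 7.1.2, state that the wWOCF windows apply to those doses. For drugs with no listed window, such as NSAIDs or acetaminophen, use the existing rule for unplanned rescue, set before the blind is broken. Keep the late score.
3. State that doses after 72 h count toward neither opioid consumption nor time to first opioid rescue.

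The cost is up to 4 more hours of medication recording per subject, edits to four recording passages and short additions to the SAP. No score is discarded and no treatment is delayed. I would not require the 72 h score to be taken before any change of regimen: that could hold back non-protocol analgesics by up to 4 h, which is out of proportion to an effect of this size.
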